7 STUDY SCHEDULE

Refer to Appendix A for the Schedule of Events.

7.1 Screening

Recruitment/Enrollment (Day -56 to -1)

- Recruit potential caregiver participants using an in person approach at several venues including parent-teacher meetings, open house, curriculum nights, health fairs, and at prearranged convenient times during school drop off /pick up of the child. An additional approach is to send home a recruitment packet containing a recruitment flyer and consent forms to increase recruitment.
- Review inclusion/exclusion criteria to determine eligibility (**Refer to Sections 5.1, 5.2**).
- Review the written consent form (**Refer to Section 15.3**) with the potential participant; study staff signs the consent form acknowledging that informed consent was reviewed and caregiver signs acknowledging consent was obtained.
- Obtain (in person or by mail) demographic and contact information and responses to the following questionnaires: Baseline Illness Perception Questionnaire – Revised for Dental (IPQ-RD) and Baseline Caregiver Questionnaire.
- Telephone contact with caregiver if baseline questionnaires are not filled out and returned 2 days after receipt.

7.2 Baseline Dental Screening

Baseline Dental Screening Visit (Visit 1, Day 0-5)

- Obtain assent of child prior to dental screening examination.
- Perform initial child dental screening examination at child's respective elementary school.
- Record results of dental screening examination.
- Randomize caregivers of children with restorative referral outcome on screening to 1 of 5 study arms.
- Send referral letter packets to caregiver with child and by mail.
- Telephone contact with caregivers (within 48 hours of screening examination) to confirm receipt of referral letter packet.

- Resend referral letter packets to caregivers as necessary.
- Follow-up telephone contact with caregivers to confirm receipt of secondary letter.

7.3 Follow-up Visit

Follow-up Visit (Visit 2: 2 weeks after initial dental examination)

- Telephone contact with caregivers (2 days before questionnaires sent) to confirm contact information and let them know the questionnaires will be sent to them.
- Mail 2-week follow-up questionnaires (IPQ-RD and Caregiver) to caregivers.
- Telephone contact with caregivers (7 days after questionnaires are received) to remind them to return questionnaires.
- Additional telephone contacts (1-2 reminders), and then ask for assistance from the teacher.
- Record unanticipated problems or adverse events as reported by subject or observed by investigator.

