Confounders	Child's age, race, dental visit Caregiver socio-demographics (age, race, SES, education, marital status)	Baseline	NHANES IV
Subject compliance with Intervention	
 • Whether the referral letter (and DIG) was received (generic code) • Whether the referral letter (and DIG) was read/understood (Postcard) 	Within 2 days after Baseline dental exam	

1. **Baseline:** prior to screening dental exam; **At randomization:** after baseline dental screening exam; **Two-weeks:** Two weeks after randomization; **Exit:** two weeks before end of school year dental exam

2. Caregiver self-efficacy and subjective norms will also be considered as potential **mediators** in the additional mediational analyses, and will be measured at the **Exit** in addition to **Baseline**.

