Arm 5 (N=204): The fifth arm (control) is the modified standard letter (based on November 2007 guidelines for Oral Health Screening in Ohio Schools). This letter is consistent with others used across the country and will be used in both the Ohio and Washington sites.

All letters will be sent home with the child on the day of the screening and mailed to the caregiver’s address within 24 hours. The address will be obtained during recruitment and verified with the school secretary.

A description of the recruitment, enrollment, randomization, and follow-up is below:

Caregivers will be recruited at the beginning of the school year and complete baseline forms (consent form, Illness Perception Questionnaire-Revised for Dental (IPQ-RD) questionnaire, and caregiver questionnaire) prior to dental screening and randomization (Figure 4.2.2). Children in K-4 whose parents have consented/assented will receive a screening exam in early October 2015. Caregivers whose children have no cavities or who have emergent needs will not participate further in the clinical trial. The baseline data from discontinued child and caregiver participants will be used only for baseline descriptive comparisons.

At the same time following screening exams eligible caregivers of children with restorative referrals will be randomized. Caregivers will be followed at 2 time points: 2 weeks after the receipt of the intervention letter and 2 weeks prior to the final (exit) study visit examinations in May 2016 (approximately 7 months after the initial dental exam). At both time points caregivers will complete the IPQ-RD and the caregiver questionnaire. A small sub-sample of 60 caregivers will be randomly

sampled from arms 1, 2 and 5 (20 per arm), to complete the IPQ-RD 1 month after enrollment for reliability purposes. All questionnaires will be mailed to the home address and asked to be returned to the class-room teacher or the outreach staff. Further, outreach staff will ensure that the caregivers received and returned the materials through follow-up calls. The schedule and scripts for the call are contained in the MOP (Table 6.1 and Appendix 6). Children will have a follow-up dental exam in May 2016.

[figure not shown]

Figure 4.2.2 Flowchart for Recruitment, Enrollment, and Randomization

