In addition to assessing the overall effects of the interventions, we will investigate the mechanisms (or paths) through which interventions impact dental care receipt. As represented in Figure 1, we hypothesize that a significant portion of the intervention effect will occur via a three-link path: intervention will affect caregiver illness representation which will in turn affect behavioral intention which will in turn affect dental care receipt. Initially, we will consider an overall average score for caregiver illness representation and for behavioral intention. We have previously developed a generalized causal mediation analysis methodology (Albert and Nelson, 2011) which we can use to estimate and test this specific path effect. It is possible that other paths may also be involved – namely, a direct path (possibly involving unidentified mediators) from intervention to dental care receipt, and paths through either caregiver illness representation or behavioral intention alone. We will therefore decompose the overall effect, and estimate the contribution of each of the four possible paths. For each (broadly defined) mediator, we may be interested in examining multiple components (e.g., summary scores or factors representing specific constructs for caregiver illness representation, and the two questions of behavioral intention). We may thus handle each mediator in our model as multidimensional (that is, a vector of latent or observed variables). In addition, we will consider a further refinement of the model, and decomposition of the intervention effect, by allowing separate paths through the individual components of each mediator. The 2-week measurement time for the mediators reflects the hypothesized time of maximum impact of the intervention. However, we will make use of the 7-month measurements of the mediators to assess any changes in the effect of the intervention over time, as well as the relationship between the mediators (at alternative times) and dental care receipt.

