14.2 Study Intervention and Study Questionnaires

Quality Assurance Procedures

The **Outreach Workers and study staff**, who will facilitate the receipt of intervention letters and access to the study questionnaires, will attend a 2-day in person training on the conduct of the study protocol and logistics (See MOP Section 5). In-class training will incorporate the topics of human subject protection, Good Clinical Practice (GCP), and the study protocol. A segment of the training will emphasize how data management procedures promote high-quality data collection and reduce threats to fidelity. Focus will be placed on following the procedures that have been outlined in the protocol, principles of data management, and forms administration procedures. All types of documentation will be discussed including forms filled out by participants and study forms completed by staff. For each, the purpose, instructions for completion and procedures to maintain accuracy will be addressed. As part of tracking and managing study records, staff members will learn how to document activities that occur with subjects, update study documentation, and use the tracking logs. As part of the training, the study staff will be certified in the topics presented to ensure their comprehension of the expectations.

Fidelity of the **Outreach Workers'** telephone contacts with caregivers will be assessed throughout the study to ensure that they have not provided additional information to the childrens' caregivers that might influence the outcome. (Refer to MOP Section 5).

For reliability purposes and to further assess the stability of the IPQ-RD presumably after visits to the dentists (between 2 and 4 weeks), we will randomly select a sub-sample of 60 caregivers (20 each in arms 1, 2, and 4) to respond to the IRQ-RD after 4 weeks.

Quality Control Procedures

The first ten (10) **Outreach Workers** telephone contacts (reminder calls to return the questionnaires) will be audio recorded in digital media and reviewed. Then, the first ten (10) of the following remaining type of call will be recorded and reviewed for each Outreach Worker (confirmation of receipt of referral letters-calls #2, and reminders to return completed questionnaires-calls #4 and #6). At the beginning of the study, the **Project Coordinators** will review the first ten telephone contacts to ensure fidelity of the calls and accuracy of data recording.

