32d. Diet or eating habits can cause cavities in a child	1	2	3	4	5
32e. Chance or bad luck can cause cavities in a child	1	2	3	4	5
32f. Poor dental care can cause cavities in a child	1	2	3	4	5
32g. Something a parent/caregiver does can cause cavities in a child	1	2	3	4	5
32h. A parent/caregiver's negative thoughts can cause cavities in a child	1	2	3	4	5
32i. Family problems or a parent/caregiver's worries can cause cavities in a child	1	2	3	4	5
32j. A parent/caregiver's feelings (feeling down, anxious) can cause cavities in a child	1	2	3	4	5
32k. A child's lack of ability to fight off infections can cause cavities	1	2	3	4	5

Site: _____ ID#_____

33. Please list in order the three most important things that you believe cause cavities in children. You may use any of the items from the previous question or you may have other ideas of your own.

[figure not shown]
The most important causes for me are:

1st _____

2nd _____

3rd _____

Family Access to Dentist Study

Study Site: _____ ID#: _____

Caregiver Questionnaire-2-week Follow-up

1. TAKING YOUR CHILD TO THE DENTIST**1.1 Did your child visit the dentist after the school dental screening?**

- a) Yes → Please GO TO Question 1.2
- b) No, but I have made an appointment with the dentist → Please SKIP TO Question 1.5
- c) No, and I have not made an appointment with the dentist → Please SKIP TO Question 1.6

If you answered YES to Question 1.1 above, please answer the following questions:

1.2 What is the name of the dental clinic / dentist where you took your child?

1.3 Did you take the referral letter (from the school dental screening) with you to the dentist?

- a) Yes
- b) No

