Please circle the number of the best answer	Strongly Agree	Agree	Neither Agree nor Disagree	Disagree	Strongly Disagree
	1	2	3	4	5
32a. Stress or worry can cause cavities in a child					
32b. Cavities runs in families					
32c. A germ or virus can cause cavities in a child					
32d. Diet or eating habits can cause cavities in a child					
32e. Chance or bad luck can cause cavities in a child					
32f. Poor dental care can cause cavities in a child					
32g. Something a parent/caregiver does can cause cavities in a child					
32h. A parent/caregiver's negative thoughts can cause cavities in a child					
32i. Family problems or a parent/caregiver's worries can cause cavities in a child					
32j. A parent/caregiver's feelings (feeling down, anxious) can cause cavities in a child					
32k. A child's lack of ability to fight off infections can cause cavities					

Site: _____ ID#: _____

33. Please list in order the three most important things that you believe cause cavities in children. You may use any of the items from the previous question or you may have other ideas of your own.

The most important causes for me are:

1st _____

2nd _____

3rd _____

Family Access to Dentist Study

Caregiver Questionnaire	June 29, 2015
	Final Follow-up

1

Study Site: _____ ID#: _____

Caregiver Questionnaire-Final Follow-up

Date of Interview: _____

Interviewer's initials: _____

month day year

1. BACKGROUND INFORMATION**1.1 Your marital status.** Please mark only one with an X.

Married	_____	Divorced	_____
Single	_____	Separated	_____
Common law	_____	Widow	_____
Unknown	_____		

1.2 If you are the parent, does your child's other parent live with you?

Yes	_____
No	_____

1.3 Your education.**1.3a How many years of schooling have you completed?** _____ years**1.3b Your highest level of education completed.** Please mark only one with an X.

Graduate degree (PhD, MD, JD, MA)	_____
Some graduate school	_____
College/University degree	_____
Some college	_____
High school diploma/GED	_____
Grade 10-11	_____
Grade 7-9	_____
Grade 1-6	_____
Unknown	_____

1.4 What is your current occupation(s)? Please write in your response(s) below.

2

Study Site: _____ ID#: _____

Caregiver Questionnaire-Final Follow-up

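### The plan does not ensure that the 2-week IPQ-RD score precedes dental care, so the mediation analysis can count an effect of care on perception as an effect of perception on care

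*Combined protocol and SAP*

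**What the plan says.** **Timing.** Section 7.3 sets the visit as "Follow-up Visit (Visit 2: 2 weeks after initial dental examination". The Table 3.2.1 footnote instead says "Two weeks after randomization", and section 4.2 says "2 weeks after the receipt of the intervention letter". Under 7.3 both questionnaires are mailed, a reminder call follows 7 days after receipt, and then: "Additional telephone contacts (1-2 reminders), and then ask for assistance from the teacher". Neither 7.3, Table 3.2.1, section 8, section 12.4 nor Appendix A gives a return window, a last day or a rule for late forms.

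**Expected visits.** Section 14.2 plans a 4-week repeat of the IPQ-RD in a sub-sample of 60 caregivers, to assess its stability "presumably after visits to the dentists (between 2 and 4 weeks").

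**Analysis.** Section 12.4 posits a path from letter to illness perception to intention to care, and states: "The 2-week measurement time for the mediators reflects the hypothesized time of maximum impact of the intervention". It has no rule for a score obtained after a visit.

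**Forms (Appendix C).** Item 1.1 of the 2-week caregiver questionnaire asks: "Did your child visit the dentist after the school dental screening"? The baseline and final caregiver questionnaires carry a "Date of Interview" line. No such line appears in the 2-week caregiver questionnaire or the 2-week IPQ-RD as supplied, in English or Spanish.

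**The concern.** Mediation requires the mediator to be measured before the outcome it is meant to explain. A dental visit may itself change how a caregiver answers questions about the seriousness, causes and control of cavities. If some caregivers complete the IPQ-RD after the visit, attenders will score differently because they attended, and the analysis will credit perception with producing attendance. The secondary objective is to understand how the letters work, so this bears directly on that conclusion.

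It applies to the IPQ-RD because every caregiver answers it, whether or not the child has been seen.

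**Working it through.** The plan states no figure on this point, so there is none to reproduce. Two checks follow.

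**1. Calendar.** From 7.3: mailing on day 14 and a first call 7 days after receipt. Mail time *m* (0-4 days) and the gap *g* between later contacts (2-7 days) are assumptions.

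| Step | Formula | g = 2 | g = 7 |
|---|---|---|---|
| First reminder | 14 + m + 7 | day 21-25 | day 21-25 |
| After two more calls | 21 + m + 2g | day 25-29 | day 35-39 |
| Through the teacher, one gap later | 21 + m + 3g | day 27-31 | day 42-46 |

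Weeks 2-4 are days 14-28. A form returned in response to a reminder therefore comes back within or after that period. A return date is not a completion date, and without a date line the two cannot be separated. Counting from receipt of the letter, as in 4.2, moves these days later when a letter has to be resent.

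**2. Effect on a mediation test.** Inputs from section 12.2: care rates of 19% (standard letter) and 37% (CSM letter), 204 caregivers per arm, IPQ-RD SD 27, and a letter effect of 10 points (10/27 = 0.37 SD). Assumed: a share *f* of attenders completes the form after the visit, and the visit lowers the score by *d*. IPQ-RD has no true effect on care.

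The false arm difference in IPQ-RD produced by visits alone is f x d x (difference in care rates). With f = 0.3 and d = 10 points:
- 19% vs 37%: 0.3 x 10 x 0.18 = 0.54 points
- 19% vs 57%: 0.3 x 10 x 0.38 = 1.14 points

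These are small. The larger distortion is in the link from IPQ-RD to care. At a nominal 0.05 with 204 per arm, that link tests significant with probability 0.05-0.06 at f = 0.1, 0.07-0.19 at f = 0.3 and 0.13-0.41 at f = 0.5, for d of 5-10 points and either comparison above.

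Next, let the letter truly shift IPQ-RD by 0.37 SD, and declare mediation when both links are significant (linear regression for letter to IPQ-RD; logistic regression adjusted for arm for IPQ-RD to care). For 19% vs 37%, repeated simulations gave these ranges:

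| Share of attenders with a post-visit form | Visit shift 0.37 SD | Visit shift 0.74 SD |
|---|---|---|
| 0% | 4-5% | 4-5% |
| 10% | 5-6% | not tabulated |
| 20-50% | 9-36% | not tabulated |
| 30-50% | 13-36% | 46-90% |

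Dropping the post-visit forms returned the rate to about 4-6%.

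**The case against.** **The order is already recorded.** Item 1.1 captures a prior visit by self-report, the final questionnaire asks the month of the visit (item 5.2), and contacts are logged in a tracking database. So a reader who infers that the order cannot be known goes too far. What stands is narrower. Section 12.4 never uses item 1.1. That item is on the caregiver questionnaire, so it orders the separate IPQ-RD only if both were completed together. A month of visit cannot be set against an undated form.

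**It does not cover both mediators.** A reader might extend the point to behavioral intention. The documents do not support that: items 1.6a-b of the 2-week form go only to caregivers with no visit and no appointment. For the others the intention score is missing, not measured after care. That is a separate problem.

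**Lateness is not the whole mechanism.** Item 1.1 allows a visit before an on-time form, so a closing date alone would not solve the problem. This is correct.

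**The 14.2 timing is thin evidence.** The sentence concerns a reliability sub-sample, and the parenthesis may describe the retest interval. Care can be sought over 7 months. If visits were spread evenly over about 30 weeks (an assumption), 3/30 to 4/30, or 10-13%, would precede a form completed in week 3-4. With 5-13% affected, false mediation is 5-8% for a 0.37 SD shift and 7-14% for 0.74 SD.

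**Some sources are not to hand.** The call schedule is in the Manual of Procedures, and a separate statistical analysis plan is listed under Supplemental Materials; either might hold a cut-off. The cover of the English 2-week caregiver form is not in the supplied text (the Spanish cover shows only a version date). The absence is therefore shown for the protocol and the forms as supplied, not beyond them.

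**Conclusion.** The point holds for the IPQ-RD mediator. Followed as written, the plan can place perception measured after care on the path leading to care, and it pre-specifies nothing to detect this.

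The size is uncertain. It is negligible if about 10% of attenders are affected and a visit shifts the score by 0.37 SD, and material (about 9-35%) if 20-50% are. Rates near 50% and above appeared only with a 0.74 SD shift, twice the plan's own letter effect, and 30-50% affected; the documents support neither. The test used is a single-mediator joint-significance rule, not the four-path decomposition in 12.4, so the rates are illustrative.

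A reader might infer that the secondary objective would be falsely declared met. The plan sets no success criterion for that objective, so the risk is a misleading account of mechanism. Nor is the main result in doubt: the primary outcome comes from the dental examinations and does not use these forms.

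**What to change.** 1. **Forms.** Add a completion-date line to the 2-week IPQ-RD and the 2-week caregiver questionnaire, in both languages.
2. **Section 7.3.** State a last day for a form to count as the 2-week value, counted from a single start point used consistently in 7.3, 4.2 and Table 3.2.1. Keep collecting later forms and flag them.
3. **Section 12.4.** Pre-specify a sensitivity mediation analysis for IPQ-RD that excludes forms completed after a visit (item 1.1 answered Yes) or outside the window. Report it beside the all-forms analysis, and draw a mechanism conclusion only if the two agree, with agreement defined beforehand.

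The cost is one printed line per form and a few sentences. Section 5.3 plans a second recruitment year, so the revised forms could still serve those families.

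The downside is that the sensitivity set is smaller and is selected on an event after randomization that the letters are meant to change. It drops the fastest responders, possibly unequally by arm. It should therefore stand beside the all-forms analysis and not replace it. It does not repair the missing intention scores, so it serves the IPQ-RD link and not the full three-link path.

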7.4 Final Study Visit

Final Study Visit (Final Visit: approximately 7 months after initial dental examination)

- Telephone contact with caregivers (2 days before questionnaires sent) to confirm contact information and let them know the questionnaires will be sent to them.
- Mail Final follow-up questionnaires (IPQ-RD and Caregiver) to caregivers.
- Telephone contact with caregivers (7 days after questionnaires are received) to remind them to return questionnaires.
- Perform final child dental screening examination at child's respective elementary school.
- Record results of dental screening examination.
- Record unanticipated problems or adverse events as reported by subject or observed by investigator.

7.5 Withdrawal Visit

Early Withdrawal or Termination Visit (any time investigator withdraws participant or participant terminates from the study)

- In-person contact
- Record any event reported by participants that the PI determines to be an unanticipated problem.
- Debrief about the intervention.
- Obtain responses to the nearest study questionnaires (IPQ-RD, caregiver)

8 STUDY PROCEDURES/EVALUATIONS

The following are the various study procedures and evaluations that will be done during the study:

Administration of questionnaires (IPQ-RD and caregiver questionnaires including demographic information) for caregiver and child information (See Section 3.2, Table 3.2.1; see Appendix C): Caregivers will be asked to complete questionnaires at three time points (baseline prior to screening, 2 weeks after the dental screening examination, and at the end of the school year).

Dental examinations for baseline caries status and primary study outcome: Exams will be performed on the children whose caregivers have consented to their participation. The dental examinations will be done according to the standard caries detection and assessment system termed ICDAS (International Caries Detection and Assessment System). The initial examination (approximately 2 months after the beginning of the school year) will determine a child's need for restorative care which is an inclusion/exclusion criterion for study continuation and randomization. The final examination (approximately 1 month prior to the end of the school year) will be used for the primary study outcome for children enrolled in the RCT.

Administration of the intervention (referral letters) (See Section 6 – Study Intervention): The letter will be sent home with the child and mailed to the caregiver. Confirmation that the letter was received will be obtained through telephone contacts.

